Comparing Intubation rates in the delivery room by interface

NCT05609773

July 19, 2022

Research Proposal Department of Pediatrics

Project Title: Comparing intubation rates in the delivery room by interface

7-19-2022

Study Personnel:

Name, degree	Role	Employer
[name]	Co-PI	UICOMP
[name]	Co-PI	UICOMP
M. [name]	Investigator	UICOMP
[name]	Mentor	UICOMP
[name]	Collaborator	UICOMP

Study Sites:

OSF - St. Francis Medical Center - Peoria St. Jude Midwest Affiliate

Unity Point Methodist/Proctor UICOMP

Other:

Anticipated study duration after start: 1 year

Needed services:

Statistician Healthcare Analytics

Funding source:

The research specified in this protocol will not be funded.

The research specified in this protocol is funded by a pharmaceutical/device company.

The research specified in this protocol is funded through NIH

- Other: applying for department and CHOI grant funding
- This study has been reviewed with the relevant division(s) or division head(s).
- I request detailed feedback/mentorship from the Research Facilitation Committee for this project.

Background and rationale

Although the majority of premature neonates < 30 weeks gestation require positive pressure ventilation (PPV) at birth, the optimal interface to provide PPV has not been determined. Preferably this support would be provided by non-invasive means to prevent the development of bronchopulmonary dysplasia. Resuscitation with a face mask, single nasal tube, nasal prongs, and/or LMA are all approved methods of resuscitation per NRP as of 2010. Face masks have been associated with more dead space, air leak and airway obstruction however are the most commonly used interface. Recently, the Trigeminal Cardiac Reflex has been described, which can be induced with the placement of a facemask, resulting in bradycardia and apnea. Bi-nasal prongs (RAM cannula) have been found in studies to be associated with lower intubation rates in the delivery room (down to 24 weeks gestation), less need for epinephrine, chest compressions, and subsequent invasive ventilation. In addition to the potential practical advantages of bi-nasal prong resuscitation, there is evidence to suggest that ventilation through the nose may stimulate the subepithelial receptors of the upper airways causing an increase in respiratory rate and depth.

Both binasal prongs and face masks are acceptable by NRP and have been utilized for neonatal resuscitation at OSF SFMC since 2016, however the choice is by provider preference with rare use of the bi-nasal prongs. Also, historically we have provided constant positive airway pressure (CPAP) during delayed cord clamping with a facemask by the OB team who needs to remain sterile during a C/S (majority of premature deliveries). Thus, nearly all babies have had some exposure to a facemask during the initial resuscitation period.

For our prospective study we will sterilize facemasks, bi-nasal prongs, and tubing. A neonatal provider will scrub and don sterile gown and gloves to be able to provide the infant with the CPAP utilizing the study interface during delayed cord clamping. That same interface will be continued during resuscitation measures after delayed cord clamping is complete.

The interface utilized in the delivery room to provide resuscitation has been recorded in the Vermont Oxford Database since 2018. On retrospective review of patients born < 30 weeks' gestation, 7/30 of neonates resuscitated with bi-nasal prongs were intubated in the delivery room (23%) and 114/136 of neonates resuscitated with facemask were intubated in the delivery room (84%). There were 33 infants in which both a facemask and bi-nasal prongs were utilized during initial resuscitation as well, 13 of required intubation (39%). However, we are unable to determine from the database which interface was utilized first. Also, prior to 2021, only one neonatologist was utilizing bi-nasal prongs thus it is difficult to determine if the difference is entirely due to the interface alone.

Specific Aims/Objectives

We hypothesize that there will be at least a 40% reduction in the rate of intubation for patients born < 30 weeks' gestation when bi-nasal prongs are utilized for neonatal resuscitation vs face mask.

Research Design and Methods

1. Subject population

Subject identification/recruitment:

All patients born at OSF SFMC < 30 weeks' gestation

Inclusion/exclusion criteria, including age:

Inclusion: all resuscitated infants < 30 weeks' gestation born at OSF SFMC

Exclusion: diagnosis of congenital diaphragmatic hernia, no PPV needed, or no resuscitation desired due to major congenital anomalies or peri-viable status

Estimated sample size:

Hypothesis: 40% reduction in intubations in the delivery room

Baseline intubation rate for facemask resuscitation in neonates < 30 weeks from 2018-2020: ~80% (retrospective intubation rate for ram cannula resuscitation 23%)

alpha 0.05, beta 80%

Estimated sample size = 42 patients

Estimated M:F ratio:

1:1

2. Study design (specify study type, any randomization or control groups)

Prospective stratified randomization with separate blocks for neonates with a gestational age < 25 0/7 weeks and those 25 1/7 weeks to 29 6/7 weeks gestation.

3. Procedures (step by step description of each part of the study, tools to be used, any subject compensation)

- 1) Consent would be obtained prior to birth by neonatologist
- 2) Randomization would occur prior to delivery
- 3) Patients receiving non-randomized apparatus will be considered a protocol violation.
- 4) CPAP will be set up prior to either c/s or vaginal delivery utilizing either an appropriately sized face mask or ram cannula. Sterile packets with tubing and prongs or a facemask will be supplied for C/S.

a) Bi-nasal prong Resuscitation

- i) Settings on T-piece are set to PIP of 22, PEEP of 6, Flow of 10 L, FiO₂ 30%. (Settings are slightly higher than facemask to account for known leak with RAM cannula so the pressure seen by the lungs should be equivalent between the nasal prongs and facemask.)
- ii) Immediately after delivery, place the RAM cannula in correct position with the prongs in the nares (prongs should face down into the nasopharynx) and tighten the strap around the head.
- iii) If the neonate is actively breathing, provide CPAP via the RAM cannula and T piece
- iv) If the neonate is apneic or ineffectively breathing, provide PPV via the RAM cannula and T piece at a rate of 40-60 breaths per minute by holding the cannula with your thumb and closing the mouth with your middle finger to ensure a proper seal
- v) If the heart rate starts to increase, continue with resuscitation per NRP guidelines
- vi) If the heart rate does not increase appropriately, troubleshoot the RAM cannula:
 - (1) Suction nares and mouth
 - (2) Maintain Closed mouth
 - (3) Adjust RAM Cannula in nose to ensure seal
 - (4) Reposition head and neck to open airway
 - (5) Increase pressure by increments of 2 until adequate chest rise is seen or at a PIP of 30
 - (6) Alternative Airway (intubation)
- vii) When 60 seconds of delayed cord clamping is complete (if appropriate to perform delayed cord clamping) - Patient will move on the bed to the resuscitation room to complete resuscitation as above. Pulse oximeter to be placed on the right wrist and EKG leads placed in the appropriate position.

a. Face mask resuscitation

- i. Settings on T-piece are set to PIP of 20, PEEP of 5, Flow of 10 L, FiO₂ 30%.
- ii. After delivery, place the face mask in the correct position on the face, bringing the chin to the mask

- iii. If the neonate is actively breathing, provide CPAP via the Face Mask and T piece
- iv. If the neonate is apneic or ineffectively breathing, provide PPV via the Face Mask and T piece at a rate of 40-60 breaths per minute
- v. If the heart rate starts to increase, continue with resuscitation per NRP guidelines
- vi. If the heart rate does not increase appropriately, troubleshoot the Face Mask:
 - 1. Adjust the Face Mask
 - 2. Reposition the head and neck to open airway
 - 3. Suction mouth, then nares
 - 4. Open Mouth
 - 5. Increase pressure by increments of 2 until adequate chest rise is seen or at a PIP of 30
 - 6. Alternative airway (intubation)
- vii. When 60 seconds of delayed cord clamping is complete (if appropriate to perform delayed cord clamping) - Patient will move on the bed to the resuscitation room to complete resuscitation as above. Pulse oximeter to be placed on the right wrist and EKG leads placed in the appropriate position.

4. Statistical Analysis Plan (sample size, power justification, specific tests to compare variables)

Primary objective: 40% reduction in intubation rate from resuscitation with facemask vs binasal prongs.

Secondary objectives: incidence of chest compressions and epinephrine in the delivery room, incidence of chronic lung disease, mortality, severe IVH (grade 3-4), severe ROP (stage 3-5) - all would be compared with chi-square testing. Would also analyze average hematocrit and base deficit (if a blood gas is obtained) after admission to the NICU and compare groups via student t-test.

5. Consent procedures (if applicable, or rationale for waiver of consent; list study personnel responsible for consent)

Parents would be consented prior to birth. If parents do not consent for inclusion in the study, the neonate would be resuscitated per routine by NRP guidelines utilizing the interface of provider preference.

6. Risks to subjects/Minimization of Risks (including alternatives to treatment, and

any benefits to participation)

Patients would have minimal risk. Both interfaces are acceptable for use by NRP. Thus, only risk would be in regards to the storage of patient information.

7. Measurement

Data to be collected:

See excel spreadsheet attached

List any additional data elements that will need to be accessed for the study, but not collected (eg when selecting patients from the EMR): None

If specimens/sample will be obtained, described how they will be labelled including any patient identifiers: N/A

8. Data Storage Plan (where/how will data be stored, accessed, and protected; paper records vs Excel/REDCap)

Data will be stored on REDCap

Duration of data storage after study completion: 3 years

Plan for deletion of data or removal of identifiers: Patient ID will be removed once all data is collected and finalized

9. Alignment (How does this project align with or add value to department/institutional objectives?)

The project is well aligned with multiple division goals - reducing intubation rates in the delivery room has the potential of avoiding CPR, allowing for LISA administration which has been associated with lower rates of severe IVH and chronic lung disease than other modes of surfactant administration. The project would also contribute significantly to the literature regarding the optimal interface device in the delivery room.

10. Goals for Publication/Presentation of Results (include plans for authorship, guidelines can be found [here](#))

Will plan to publish results and present at conferences such as PAS and AAP.

References

Aziz, Khalid, et al. "Part 5: Neonatal Resuscitation 2020 American Heart Association Guidelines for Cardiopulmonary Resuscitation and Emergency Cardiovascular Care." *Pediatrics*, vol. 147, no. Supplement 1, 2020, doi:10.1542/peds.2020-038505e.

Biniwale, Manoj, and Fiona Wertheimer. "Decrease in Delivery Room Intubation Rates after Use of Nasal Intermittent Positive Pressure Ventilation in the Delivery Room for Resuscitation of Very Low Birth Weight Infants." *Resuscitation*, vol. 116, 2017, pp. 33–38., doi:10.1016/j.resuscitation.2017.05.004.

Capasso, Letizia, et al. "A Randomized Trial Comparing Oxygen Delivery on Intermittent Positive Pressure with Nasal Cannulae versus Facial Mask in Neonatal Primary Resuscitation." *Acta Paediatrica*, vol. 94, no. 2, 2007, pp. 197–200., doi:10.1111/j.1651-2227.2005.tb01890.x.

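### The exclusion for infants who need no PPV can be judged only after randomisation with the assigned interface in use, so applying it removes randomised infants on an event the interface may influence

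*Protocol*

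**What the plan says.** **Eligibility** (Research Design and Methods, section 1). The inclusion line begins "Inclusion: all resuscitated infants < 30 weeks". The exclusion line begins "Exclusion: diagnosis of congenital diaphragmatic hernia, no PPV needed, or no resuscitation desired", and its last item in full is "no resuscitation desired due to major congenital anomalies or peri-viable status".

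**Timing** (section 3, Procedures). Consent is obtained before birth, and "Randomization would occur prior to delivery". In each arm, step ii places the assigned interface after delivery. Steps iii and iv then divide care by breathing. For prongs, step iii reads "If the neonate is actively breathing, provide CPAP via the RAM cannula and T piece"; an infant who is apneic or breathing ineffectively gets PPV. The face mask steps are parallel. The Background adds that a scrubbed provider will "provide the infant with the CPAP utilizing the study interface during delayed cord clamping".

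**Question.** The Specific Aims state a "reduction in the rate of intubation for patients born < 30 weeks" of gestation, without restriction to infants given PPV. The Background frames the open question as which interface is best for giving PPV, and says that most, not all, infants under 30 weeks need it.

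**The concern.** An exclusion is harmless when it is settled before allocation or cannot be affected by it. This one is neither. PPV need is unknown at randomisation and is decided once the assigned device is on the infant. The protocol itself gives reasons why the device could change that decision, and the staff who decide can see which device is in use.

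Infants removed in this way would mostly be infants who were not intubated. If the interface shifts how many are removed in each arm, the remaining groups are no longer the groups that were randomised. The resulting bias could not be separated from the effect of the interface. With 42 infants planned, a few removals matter.

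The word resuscitated in the inclusion line is a lesser, ambiguous case. Beside the item on resuscitation not being desired, it may mean resuscitation intended, which is known before birth, or resuscitation given, which is not. The point rests on the PPV exclusion, which has no such double reading.

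**Working it through.** **Order of events.** (1) Consent and randomisation, before birth. (2) Assigned interface placed after delivery. (3) Breathing assessed: CPAP only, or PPV. (4) Intubation, if needed. The exclusion depends on step 3; allocation is at step 1 and exposure at step 2.

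**Inputs from the protocol.** Mask intubation rate about 80%; a 40% reduction; alpha 0.05; power 80% (labelled beta); 42 patients.

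**Assumptions.** Two-sided test; 1:1 allocation, so 21 per arm; every intubated infant had PPV; and PPV need by arm, which the protocol does not give.

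**The plan's own figure.** For 80% vs 40% at 80% power, the normal approximation gives

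- unpooled: (1.96 + 0.842)² × (0.80×0.20 + 0.40×0.60) / 0.40² = 19.6 per arm, or 40 in total after rounding up;
- pooled under the null: 22.3 per arm, or 46 in total.

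The stated 42 lies between these, so the 40-point reading is used below. Power at 21 per arm is 77% (pooled formula).

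**Effect of the exclusion.** Take 80% and 40% as the rates among all randomised infants. Among infants given PPV:

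- analysed rate = intubation rate / PPV need;
- analysed number = 21 × PPV need;
- observed risk ratio = true risk ratio × (PPV need, mask / PPV need, prongs).

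For 95% (mask) and 75% (prongs): 0.80/0.95 = 84.2%, 0.40/0.75 = 53.3%, risk ratio 0.50 × 0.95/0.75 = 0.63.

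| Assumed PPV need, mask / prongs | Analysed rates, mask vs prongs | Difference (points) | Risk ratio | Power |
|---|---|---|---|---|
| No removals | 80.0% vs 40.0% | 40.0 | 0.50 | 77% |
| 95% / 90% | 84.2% vs 44.4% | 39.8 | 0.53 | 76% |
| 95% / 85% | 84.2% vs 47.1% | 37.2 | 0.56 | 69% |
| 95% / 75% | 84.2% vs 53.3% | 30.9 | 0.63 | 52% |
| 90% / 90% | 88.9% vs 44.4% | 44.4 | 0.50 | 86% |
| 85% / 95% | 94.1% vs 42.1% | 52.0 | 0.45 | 96% |

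**No true effect.** If 60% of all randomised infants in each arm were intubated and PPV need were 90% (mask) and 80% (prongs), the analysed rates would be 0.60/0.90 = 66.7% and 0.60/0.80 = 75.0%. That is a spurious excess of about 8 points with prongs.

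**Power if all randomised infants are kept.** If 80% and 40% describe only infants given PPV, including the others dilutes both rates:

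- 5% without PPV: 76% vs 38%, power 72% at 21 per arm; 80% power needs 25.4, so 26 per arm (52 in total);
- 10% without PPV: 72% vs 36%, power 66%; 80% power needs 28.9, so 29 per arm (58 in total).

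**The case against.** **The bias may be small.** This stands. Every PPV share above is assumed. Equal need leaves the risk ratio unchanged, and 95%/90% moves the difference by only 0.2 points.

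**The SAP may settle the analysis set.** This stands in part. An analysis set is commonly left to the SAP, so the protocol's silence on what happens to these infants is not a fault in itself. The eligibility rule, however, is stated here. An SAP that analysed all randomised infants would limit the bias but contradict that rule.

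**A question about PPV is legitimate.** It is. But allocation before PPV need is known cannot answer it without selection after randomisation, and the stated hypothesis is not limited to infants given PPV.

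Three stronger readings are tempting, and the protocol does not support them:

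- *The rule must work against prongs.* The Background leans that way: mask placement can trigger apnea, and ventilation through the nose may increase breathing rate and depth. But the prong procedure acknowledges leak with the RAM cannula and sets higher pressures to offset it. Equal delivered pressure is an expectation, so PPV need could be higher with prongs. Unblinded judgement can push either way.
- *The retrospective data show more room for removals with prongs.* The shares not intubated were 22/136 = 16% with mask and 23/30 = 77% with prongs. These infants were already recorded as resuscitated with an interface and may all have had PPV, so the figures say nothing firm about CPAP-only infants. The groups were also not randomised.
- *Equal removals raise power.* They do (86% at 90%/90%) only if 80% and 40% are rates among all randomised infants. If they are rates among infants given PPV, losing 5% or 10% from each arm lowers power to 75% or 73%. The protocol does not say which applies.

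**Conclusion.** The point holds and should be fixed. On the protocol's own sequence, the PPV exclusion is applied after randomisation, with the assigned interface in use and visible, and on an event the protocol gives reasons to think the interface may affect. This is a stated rule that can bias the primary comparison.

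The direction is uncertain and the size unknown. Under the stated assumptions, the risk ratio could move from 0.50 to 0.63 (95%/75%) or to 0.45 (85%/95%), or stay at 0.50 if need is equal. A reader might infer that the trial will understate the benefit of prongs; the text leans that way but does not establish it.

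**What to change.** Do not use the absence of PPV need to remove randomised infants. Reword the inclusion line as infants for whom resuscitation is intended before birth. Criteria the interface cannot change, such as gestation at birth and diaphragmatic hernia, can stay.

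Make the primary comparison all randomised liveborn infants who meet those criteria, in their assigned arm, with infants given no PPV and not intubated counted as non-events. Report PPV need by arm. Keep the PPV-only comparison as supportive, labelled as a subgroup defined after randomisation.

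The edit is short and changes no care, but it has two costs. The primary analysis then answers the question of interface from birth, which matches the stated hypothesis, and the PPV-only question becomes supportive. And if the planning rate of about 80% describes only infants given PPV, power at 42 drops as shown in the working. If that rate already includes CPAP-only infants, nothing is lost.

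### The sample size of 42 does not match a 40% reduction from about 80% as worded; it roughly fits 40 percentage points, and 80% is labelled beta instead of power

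*Protocol*

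**What the plan says.** The effect appears three times, always as a single percentage:

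- Specific Aims/Objectives: "at least a 40% reduction in the rate of intubation".
- Research Design and Methods, 1. Subject population, Estimated sample size: "Hypothesis: 40% reduction in intubations in the delivery room".
- Section 4, Statistical Analysis Plan: "Primary objective: 40% reduction in intubation rate from resuscitation with facemask vs binasal prongs".

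The sample size entry gives the other inputs: "Baseline intubation rate for facemask resuscitation in neonates < 30 weeks from 2018-2020: ~80" per cent, a retrospective prong rate of 23%, "alpha 0.05, beta 80" per cent, and the result, "Estimated sample size = 42 patients". Background and rationale gives a slightly different facemask rate, 114/136 or 84%.

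The protocol does not say whether the 40% is relative or in percentage points, what rate is expected with prongs, whether 42 is the total or per arm, or whether the test is two-sided. Section 2 describes "Prospective stratified randomization with separate blocks for neonates with a gestational age < 25 0/7 weeks" and a second gestational-age stratum but gives no allocation ratio. The only 1:1 in the protocol is the expected male-to-female ratio.

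**The concern.** A 40% reduction in a rate that starts at about 80% ordinarily means 0.80 × (1 − 0.40) = 0.48. Forty-two infants are too few to detect 80% v 48% with 80% power. Read as worded, the protocol claims a power it does not have for its primary objective, and the chance of missing the effect is about 40%, twice the 20% implied.

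This matters most if the trial is not significant. A reader who trusts 80% power for a 40% reduction may conclude that such a reduction has been excluded. For example, 17/21 v 12/21 intubated gives chi-square p = 0.095, but the risk ratio is 0.71 (95% CI 0.46 to 1.08), which still includes 0.60.

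Separately, beta is the type II error rate. A beta of 80% would literally mean 20% power.

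**Working it through.** **Inputs from the protocol.** Control rate p1 = 0.80, or 114/136 = 0.838 from the Background; alpha 0.05; 80% taken as power; N = 42; a 40% reduction.

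**Assumed, because not stated.** 42 is the total (21 per arm), 1:1 allocation, two-sided test, no dropout.

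**Candidate prong rates p2.** Relative: 0.80 × 0.60 = 0.48, or 0.838 × 0.60 = 0.503. Percentage points: 0.80 − 0.40 = 0.40, or 0.838 − 0.40 = 0.438.

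**Formulas for n per arm.** Let d = p1 − p2, p̄ = (p1 + p2)/2, V = p1(1 − p1) + p2(1 − p2), z_α = 1.960 and z_β = 0.842, so (z_α + z_β)² = 7.849.

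- Unpooled: 7.849 V / d²
- Pooled: [z_α √(2p̄(1 − p̄)) + z_β √V]² / d²
- Arcsine: 2 × 7.849 / h², with h = 2 arcsin √p1 − 2 arcsin √p2
- Continuity-corrected: (n/4)[1 + √(1 + 4/(nd))]², with n from the pooled formula

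**Step 1: can 42 be reproduced?** Try 80% v 40%: d = 0.40, V = 0.16 + 0.24 = 0.40, 2p̄(1 − p̄) = 0.48, h = 0.845.

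- Unpooled: 7.849 × 0.40 / 0.16 = 19.62, so 20 per arm, 40 in total
- Arcsine: 15.698 / 0.7138 = 21.99, so 22 per arm, 44 in total
- Pooled: 22.33, so 23 per arm, 46 in total

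The fit is approximate. The arcsine formula gives exactly 42 only with the 114/136 baseline (20.89, so 21 per arm).

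**Step 2: the relative reading, 80% v 48%.** d = 0.32, V = 0.16 + 0.2496 = 0.4096, 2p̄(1 − p̄) = 0.4608, h = 0.684.

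- Unpooled: 7.849 × 0.4096 / 0.1024 = 31.40, so 32 per arm, 64 in total
- Arcsine: 15.698 / 0.4672 = 33.60, so 34 per arm, 68 in total
- Pooled: 34.12, so 35 per arm, 70 in total

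**All two-sided totals for 80% power:**

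| Rates | Unpooled | Arcsine | Pooled | Continuity-corrected |
|---|---|---|---|---|
| 80% v 40% | 40 | 44 | 46 | 56 |
| 80% v 48% | 64 | 68 | 70 | 82 |
| 83.8% v 43.8% | 38 | 42 | 44 | 54 |
| 83.8% v 50.3% | 54 | 58 | 60 | 72 |

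**Step 3: power with 21 per arm.** Pooled formula: power = Φ{[d√n − z_α √(2p̄(1 − p̄))] / √V}. For 80% v 48% this is Φ{[0.32 × 4.583 − 1.960 × 0.679] / 0.640} = Φ(0.212) = 58.4%. The exact figures sum binomial probabilities over all tables with p ≤ 0.05.

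| Rates | Pooled | Arcsine | Unpooled | Exact, chi-square | Exact, Fisher |
|---|---|---|---|---|---|
| 80% v 40% | 77.4% | 78.2% | 82.6% | 78.0% | 65.4% |
| 80% v 48% | 58.4% | 60.1% | 63.0% | 60.6% | 45.2% |
| 83.8% v 43.8% | 79.1% | 80.2% | 84.3% | 80.9% | 68.4% |
| 83.8% v 50.3% | 64.7% | 66.6% | 69.7% | 67.7% | 52.6% |

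**Step 4: other readings.**

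- One-sided 0.05, 80% v 48%: 50 to 54 in total without continuity correction; 71 to 74% power at 21 per arm. Only the 83.8% baseline comes close to 42 (44 in total, unpooled).
- Retrospective prong rate, 80% v 23%: 18 to 30 in total, two-sided, so this is not the source of 42.
- 42 per arm (84 in total): 80% v 48% needs 41 per arm with continuity correction, and exact power at 42 per arm is 88.5% (chi-square) or 83.5% (Fisher). This reading fits the relative effect.

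**The case against.** The strongest reply is that no arithmetic error is shown. The number 42 is close to what 80% v 40% requires, the protocol gives its rates as plain percentages, and the 60% figure applies only to a reading that may not have been meant. That is fair as far as it goes: N is not shown to be wrong. But a reader has only the wording, and it never mentions percentage points or a target rate.

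Second, 42 per arm fits 80% v 48% about as well as 42 in total fits 80% v 40%, so the fit alone does not show which wording failed. This stands. The preference for faulting the effect rests on 42 patients reading most naturally as a total. If it was meant per arm, the protocol understates enrolment by half and still needs correcting.

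Third, the non-significant example is not specific to the relative reading. Its risk-difference interval (−4.1 to 47.3 points) also contains 40 points, and 28/35 v 21/35 (p = 0.068, risk ratio 0.75, 0.55 to 1.03) leaves 0.60 inside too. This stands: the example warns against over-reading a null result and does not by itself show the defect.

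Fourth, the hypothesis says at least 40%, and for 80% v 23% exact power at 21 per arm is 98% (chi-square). That is true, but the protocol itself cautions that the retrospective comparison is confounded by provider, and the design value is the 40% reduction.

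**Conclusion.** The concern holds. As worded, the effect and the sample size do not match. With 42 in total, 1:1 allocation, a two-sided 0.05 level and no continuity correction, power for a 40% relative reduction from 80% is about 60% (58 to 63% by formula, 61% by exact chi-square), and 80% power needs 64 to 70 infants. The same 42 give about 78% exact chi-square power for a 40-point difference, so the wording of the effect is the likely defect, though this is not proven. A one-sided test does not rescue the relative reading at the 80% baseline; reading 42 as per arm would. The label on the 80% is wrong under every reading: it is power, and beta is 20%.

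**What to change.** In the hypothesis, the sample size entry and the primary objective, state the effect as two rates. Then, according to what was meant:

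- **40 percentage points, 42 in total:** write 80% v 40%, 21 per arm, power about 78 to 80% (beta about 20%). Add that power for a 40% relative reduction (80% v 48%) is about 60%, so that a null result is not read as excluding it.
- **40% relative reduction, 42 in total:** write 80% v 48% and restate the power as about 60%.
- **42 per arm:** say so and give 84 as the total.

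In each case state the allocation ratio, the sidedness and the formula, and replace the beta entry with power.

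If 42 is the total, this changes protocol wording only and does not itself call for more infants. The price is a less favourable stated power for the relative reading. Whether 42 randomised will yield 42 analysed is a separate question, since randomisation precedes delivery and infants who need no PPV are excluded.

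### Delivery-room intubation is decided by a provider who knows the arm, on an undefined trigger, and no listed outcome counts later intubation, so avoided and deferred intubations cannot be told apart

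*Protocol*

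**What the plan says.** The estimated-sample-size entry under Protocol section 1 gives the event: "Hypothesis: 40% reduction in intubations in the delivery room". Section 4 restates it without any criterion for intubation: "Primary objective: 40% reduction in intubation rate from resuscitation with facemask vs binasal prongs".

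Section 3 gives each arm a six-step ladder. The prong ladder opens with "If the heart rate does not increase appropriately, troubleshoot the RAM cannula" and the mask ladder with "If the heart rate does not increase appropriately, troubleshoot the Face Mask". In both, step 5 raises pressure to a common PIP ceiling of 30, or until chest rise is judged adequate, and step 6 is intubation. If the heart rate does rise, care follows NRP guidelines. A pulse oximeter and EKG leads are placed in both arms, in the step after cord clamping.

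The interface is set up by arm before delivery. No blinding, independent decision-maker or adjudication is described. The secondary outcomes in section 4 are chest compressions, epinephrine, chronic lung disease, mortality, severe IVH, severe ROP, hematocrit and base deficit. Section 7 refers to an attached spreadsheet, not shown, for the data to be collected.

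**The concern.** The endpoint is an action taken by the person using the assigned interface. Identical wording in the two ladders does not secure an identical threshold when the trigger has no measurable content and the provider knows the arm. Randomisation balances which infants, and on average which providers, fall in each arm. It does not stop one provider from waiting longer, or acting sooner, with one interface than with the other.

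The cut-off at the delivery room makes this harder to see. An infant who leaves the delivery room without a tube and is intubated soon after NICU admission counts the same as one who never needs intubation. None of the listed secondary outcomes separates the two, although the background cites less subsequent invasive ventilation as a benefit of prongs. At stake is what a positive or negative result on the only powered comparison would mean.

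**Working it through.** **Inputs.**
- Mask rate: "Baseline intubation rate for facemask resuscitation in neonates < 30 weeks from 2018-2020: ~80" per cent (sample-size entry).
- Error rates: "alpha 0.05, beta 80" per cent. The second figure is read as power. Two-sided testing is assumed, because sidedness is not stated.
- Size: "Estimated sample size = 42 patients". Equal allocation is assumed, giving 21 per arm.
- Test: section 4 assigns chi-square to the secondary outcomes and names no test for the primary. The uncorrected Pearson test is assumed, with Fisher's exact test alongside.

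**The plan's own figure.** Reading the 40% reduction as percentage points (80% v 40%), the unpooled normal formula gives

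n per arm = (1.960 + 0.842)² × (0.8×0.2 + 0.4×0.6) / 0.4² = 7.849 × 0.40 / 0.16 = 19.6, so 20 per arm, 40 in total.

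The arcsine formula, with h = 2·asin√0.8 − 2·asin√0.4 = 0.845, gives 2 × 7.849 / 0.845² = 22.0 per arm, 44 in total. The stated 42 lies between them. The present point does not depend on this figure.

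**The two ladders side by side.**

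| Element | Prongs | Mask | Measurable? |
|---|---|---|---|
| Start of ladder | heart rate not rising appropriately | same words | no value, rise or time |
| Step 5 | increments of 2, to PIP 30 or adequate chest rise | same | ceiling yes, chest rise no |
| Step 6 | intubation | intubation | no criterion for moving to it |
| Heart rate does rise | NRP guidelines | NRP guidelines | no trial-specific criterion |

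**What a threshold shift could do.** Suppose the interface has no effect, and discretion alone lowers the prong-arm rate from p₁ to p₂. With a and b intubated out of 21 in each arm, the rejection probability is the sum, over all pairs (a, b) that the test rejects, of Bin(a; 21, p₁) × Bin(b; 21, p₂). The Pearson test rejects when

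z = (|a − b|/21) / √[p̄(1 − p̄) × 2/21] ≥ 1.96, with p̄ = (a + b)/42.

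| Mask | Prongs | Pearson | Fisher |
|---|---|---|---|
| 80% | 80% | 5.2% | 2.3% |
| 80% | 70% | 12.1% | 6.4% |
| 80% | 60% | 31.1% | 19.1% |
| 60% | 50% | 9.4% | 4.8% |
| 60% | 40% | 24.2% | 15.1% |

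The 60% base and the shifts of 10 and 20 per 100 are assumptions. No figure in the documents bounds them.

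**In counts.** A shift of 20 per 100 is about four infants in an arm (0.20 × 21 = 4.2). With 17/21 intubated on mask, 11/21 on prongs is already significant by Pearson: p̄ = 28/42 = 0.667 and z = 0.286/0.145 = 1.96. That is a gap of six decisions. Fisher's test needs 9/21, a gap of eight.

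**Opposite direction.** If the true rates were 80% v 40%, Pearson power would be 78%. If providers intubated 20 more prong infants per 100 than they would under a common threshold, the observed rates would be 80% v 60% and power would fall to 31%.

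**The case against.** Much of the opposing case stands, and it rules out four stronger readings.

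- A reader might infer that the trigger is unmeasured. It is not. Heart rate is monitored by pulse oximeter and EKG leads in both arms, though these are listed only after cord clamping. The trigger is undefined. The sentence also starts troubleshooting, and intubation comes last, after a pressure step with a common numeric ceiling.
- A reader might infer that nothing recorded could reveal a difference in threshold. The list of recorded items is in a spreadsheet that is not shown, so this cannot be established.
- A reader might infer bias towards prongs, since the team hypothesises fewer intubations with them. The background also says that prongs have rarely been used at the site, and unfamiliar users might intubate sooner. The documents settle neither direction.
- A reader might take the background's remark on its retrospective 23% v 84% contrast, that "it is difficult to determine if the difference is entirely due to the interface alone", as an admission of an arm-dependent threshold. It describes non-randomised data in which one neonatologist used prongs. Randomisation is a fair answer to that confounding. The remark shows only that provider practice may matter.

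It is also fair to say that the provider cannot be blinded here, and that the delivery room is the question the trial chose: it is in the title, and section 9 links avoiding delivery-room intubation to LISA administration. That justifies the primary endpoint. It does not tell a reader whether intubation was avoided or postponed. A supporting analysis could sit in a separate SAP, but section 4 already lists the outcomes to be compared and later intubation is not among them.

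Lastly, data collected only at intubation would miss infants in whom it was withheld. For that reason the main fix is to count early NICU intubations.

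**Conclusion.** The point holds in a limited form. The primary endpoint is a decision made with knowledge of the arm. Both ladders start on an undefined trigger and give no measurable criterion for the intubation step. On the outcomes listed, an arm-dependent threshold in either direction could not be distinguished from an interface effect, and an intubation moved to the NICU counts as avoided.

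The documents do not show that such a shift will occur, or how large it would be. The rates of 12% and 31% (6% and 19% by Fisher) show how sensitive a 42-infant trial is to a few discretionary decisions. They are not estimates of bias. They rest on 21 per arm, an 80% mask rate, two-sided testing at 0.05, no true effect and an assumed shift.

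**What to change.** 1. In section 4, pre-specify a supporting analysis of the primary endpoint that also counts intubation within a fixed early window after NICU admission. The investigators choose the window before any data are seen. If the effect does not persist in that analysis, limit the conclusion to delivery-room intubation and do not claim that intubation was avoided.
2. In section 3, have the investigators state their own criterion for starting the ladder and for moving to its last step, once and identically for both arms. No value is proposed here.
3. Confirm that the data sheet captures time from birth, heart rate, PIP reached and reason at each intubation. This helps to show early intubation in either arm, which item 1 cannot.

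Item 1 has a limit: it shows deferral only within the chosen window, and NICU intubation is also a clinical decision. The cost is one more table and a little more chart abstraction. The primary endpoint and sample size do not change.
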